4. PROCEDURES

The proposed study will utilize a prospective, experimental research design. We will recruit adult daily smokers with a history of panic attacks in the last year and they will be randomly assigned to either: (1) Panic and Smoking Reduction Treatment plus d-cycloserine (PSRT+DCS) or Panic and Smoking Reduction Treatment plus placebo (PSRT+PBO). Participants will be adults between the ages of 18-65 who have smoked daily for at least a year, currently smoke an average of at least 8 cigarettes per day, and report a motivation to quit smoking in the next month of at least 5 on a 10-point scale. Moreover, participants will have elevated fears of withdrawal and anxiety related bodily sensations and a tendency to regulate these feelings with smoking, as indexed by meeting or exceeding established cut-off scores on the Smoking Abstinence Expectancies Questionnaire (≥ 78), respectively. Eligible participants will be randomly assigned to either condition by the project biostatistician ([name]. – Consultant at Southern Methodist University). Primary outcome measures will be point prevalence abstinence (PPA), time to first smoking lapse, and time to smoking

relapse. Proposed mediators include panic attacks, distress intolerance, anxiety sensitivity, nicotine withdrawal symptoms, and negative affect. These variables will be assessed at baseline, weekly during the treatment phase, and at 2, 4, 8, 10, 16, and 24 weeks after quit date.

Eligibility Screening

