1	
 • Provide quit support and reinforcement • Discuss past experiences • Set quit date (Monday of Week 5) • Initiate self-monitoring (tracking smoking and noting cues for smoking) 	
 • Integrated treatment (PSRT) rationale • Education on panic-smoking link • Interoceptive exposure introduction • Interoceptive exposure practice • IE homework practice assigned 	
 • No
2	
 • Help identify high-risk for relapse situations • Discuss abstinence violation effect • Develop coping strategies • Encourage enlisting social support • Provide self-help materials 	
 • Review education on panic-smoking link • Review interoceptive exposure rationale • Cognitive restructuring • IE practice • IE homework practice assigned • Instruction to refrain from smoking 4 hours prior to Session 3 	
 • No
3	
 • Review elements discussed in Session 2 and isolate any areas of question/concern for patients 	
 • Interoceptive exposure practice • Cognitive restructuring • IE homework practice assigned • Instruction to refrain from smoking 4 hours prior to Session 4 	
 • Yes
4	
 • Discussion of upcoming quit day • Instruct on proper use of NRT 	
 • Homework practice review • Interoceptive exposure practice • Cognitive restructuring • IE homework practice assigned 	
 • Yes
5	
QUIT WEEK
 
 • Initiate NRT • Discussion of quitting experiences • Provide support 	
 • Encourage self-awareness of the role of panic-related experiences in smoking behavior and urge to smoke. 	
 • Yes

Research Proposal

	
 Anticipate high-risk situations 	
 Underscore importance of integrating exposure, non-catastrophic thinking, and education to maintain abstinence. Cognitive restructuring Interoceptive exposure 	

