6-7	
 Continue NRT Provide support Anticipate high-risk situations Develop social support for nonsmoking Lifestyle changes (e.g., stress management, healthy diet, exercise, and increasing pleasant nonsmoking activities) 	
 Cognitive restructuring Interoceptive exposure Situational exposure (i.e., avoided situations) 	
 No

Nicotine Replacement Therapy (NRT). All participants will receive Nicoderm CQ®, 24-hour transdermal nicotine patches and will be educated about the use of the patch at the session immediately prior to quit date. They will be instructed to apply one patch daily, beginning on quit date (week 5). Participants will use the 3-step tapering Nicoderm process (21-mg, 14-mg, and 7-mg). This regimen has been used in previous trials with a similar formulation of the patch (Fiore, 2000). A meta-analysis found no differences in outcome between 16- or 24-hour patches (Fiore et al., 1994). Participants who continue to smoke or lapse after quit day will not be instructed to discontinue the patch until their smoking level reaches 4 cigarettes/day for 4 days. Smokers who lapse during treatment will be encouraged to set a new quit date and continue their cessation attempt.

D-cycloserine or Placebo Treatment. All capsules will be identical in appearance to maintain the blind design of the study. Study capsules will be prepared containing: (a) 250mg d-cycloserine or (b) pill placebo. Individual doses of study medications, prescribed by [name], will to be dispensed to patients by study personnel 1 hour prior to sessions 3-5 and patients will be asked to remain in the clinic until session time. Because all pill taking is observed, no pill counts are necessary to help ensure adherence to the randomized drug condition. All medications will be stored in a locked refrigerator.

A. LOCATION

All data will be collected at the University of Texas at Austin. Upon completion of data collection, data analysis will take place at UT, Southern Methodist University (PI: [name]), the University of Houston (PI: [name]), and Boston University (PI: [name]). All data will be encrypted with numeric codes so that no identifying information will be included in analyses. Drs. [name], [name] and [name] will obtain IRB approval from their respective institutions prior to accessing the data.

B. RESOURCES

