Treatment Credibility and Expectancy. The 18-item Treatment Credibility/Expectancy Questionnaire (CEQ; Devilly & Borkovec, 2000) will be used to examine whether treatment expectancy or credibility varied between PSRT+DCS and PSRT+PBO and the relationship between these constructs and treatment response. We will administer the scale after the first treatment sessions of PSRT+DCS and PSRT+PBO protocols.

Patient Adherence. Patient adherence will be assessed by taking attendance at each session. Adherence to the nicotine patch usage will be assessed at Weeks 1-8 following the quit date.

Therapist Adherence. Each session (for those participants who give consent to be videotaped) will be videotaped and 10% will be rated shortly thereafter by independent raters to assess therapist adherence to, and competence with, the treatment protocol. Participants are not required to be videotaped and will indicate on their consent form whether or not they are willing to participate in the recording of sessions.

Research Proposal

Concurrent Treatment. Use of medications other than nicotine patch or other aids to smoking cessation and participation in any concurrent psychotherapeutic treatment will be assessed at each assessment point.

Safety Monitoring and Concerns. At each visit, participants will be asked about side effects of the study medication, nicotine patches, and treatment. Adverse Events and Severe Adverse Events forms will be utilized to track any symptoms expressed during weekly check-ins. Forms will be reviewed each visit by the study PI, and participants who report significant symptoms or adverse reactions will be interviewed separately to determine whether the patch should be discontinued or the dose reduced. Participants who discontinue the patch or change the assigned dose will continue their treatment.

AlcoBreath Screening. At each of the three study visits during which participants are asked to take medication (sessions 3-5), participants will be asked to breathe into an AlcoBreath tube in order to assess for the presence of alcohol before they are administered the study medication.

Facial recognition task

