Note. Shaded areas refer to measures of mediator variables. *These measures are completed as online questionnaires. ^{1,2} Patient adherence and therapist competence will be monitored separately and the schedule will vary. ³Adverse events will be assessed for DCS/PBO and NRT. ⁴Administered at the end of session 1. ⁵Alcohol screening will be completed prior to each of the three sessions which include DCS/PBO administration. ⁶The pregnancy test is the only one that will be completed at intake and monthly following randomization(SV2, 7, 13, 21, and 29). The remaining lab testing will only occur should the physician see fit.

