Tests of specific aims. Aim 1a: Treatment differences in slopes will indicate different rates of decrease in PPA. To determine whether there are treatment differences in PPA at any particular time point (e.g., week 24), we will center the “Time” variable in the GLMM model at that time point (Singer & Willett, 2003). **Aim 1b:** Cox proportional hazard models will be used to test for differences between treatments in relative risk of lapse and relapse, and in time to first lapse and to relapse. **Aim 2a:** The same analyses in Aim 1a will be used in MLMs to test for treatment differences in the psychological outcomes (withdrawal symptoms, negative affect, panic severity, distress intolerance, anxiety sensitivity). **Aim 3a:** The “a” paths in our mediation model (see Figure 1 in Specific Aims) will be calculated as in Aim 2a. Because we expect the “a” paths to be moderated, separate analyses will be conducted to calculate the “a” paths for each treatment condition (Tein, Sandler, MacKinnon, & Wolchik, 2004). The “c” path will be calculated as in Aim 1a. **Aim 3b:** The “b” paths in our mediation model will be the regression coefficients for the mediators when all the mediators are simultaneously added to the GLMM equation predicting PPA used in Aim 1a. **Aim 3c.** Tests of the mediated pathways will be conducted separately for each treatment condition (due to moderated mediation [Tein et al., 2004]). Significance of mediated pathways will be determined using Bayesian bootstrap mediation analysis (Yuan & MacKinnon, 2009).

Missing Data. Following Hall et al. (2001) and Enders (2011), we will use pattern mixture modeling to assess the effect of missing data. We will rerun our analyses coding for various missing data patterns (no missing data, sporadic missing, dropouts, etc.) to determine both if missingness impacts our findings and how the differences between PSRT+DCS and PSRT+PBO depend on the missing data pattern.

Power Analysis. Because we will have a sample size of 80, this application is not powered to detect small differences between treatment conditions. However, consistent with the aims of a Stage IB study, our primary goal is determining 1) the feasibility of the new intervention and 2) whether a Stage II study is warranted. Below we estimate (for the lowest powered analyses) the effect sizes (ESs) that we will be able to detect as statistically significant with 80% power.

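### Allocation appears to come before two drug-free sessions: people lost in weeks 1-2 are randomised without a capsule, and the Aim 2a time curves misplace an effect that cannot start before session 3

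*Protocol*

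**What the plan says.** **Allocation.** Protocol section 4 states that "Eligible participants will be randomly assigned to either condition by the project biostatistician", without a visit or week. Three places bear on the timing:
- The Randomization paragraph stands between the baseline visit and the intervention modules.
- Section 5, on treatment credibility, already speaks of two arms at session 1: "We will administer the scale after the first treatment sessions of PSRT+DCS and PSRT+PBO protocols".
- The footnote to Table 2 has pregnancy tests "completed at intake and monthly following randomization(SV2, 7, 13, 21, and 29". The code SV2 is not defined and may itself be the intake visit, so this is weak support.

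**Capsules.** Section 4 has them "dispensed to patients by study personnel 1 hour prior to sessions 3-5". Table 1 marks no capsule in weeks 1-2, yet those weeks already give both arms the treatment rationale, exposure work ("Interoceptive exposure introduction" and practice in week 1) and, in week 2, cognitive restructuring.

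**Outcomes.** Table 1 has "Set quit date (Monday of Week 5" as the quit day. The SAP power analysis for point prevalence abstinence (PPA) counts post-quit assessments. The psychological outcomes and mediators are measured at baseline, weekly in treatment, and at follow-up.

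**Analysis.** The SAP overview models PPA as a quadratic or exponential function of time, chosen by AIC and BIC. Arm differences at a given time come from re-centring time, with week 24 as the example. For Aim 2a, "The same analyses in Aim 1a will be used in MLMs to test for treatment differences in the psychological outcomes"; the Aim 3 'a' paths are calculated as in Aim 2a. The SAP defines no analysis set, no time origin for each model and no rule that missing means smoking. Neither document gives a drop-out rate before session 3.

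**The concern.** The trial asks whether d-cycloserine adds to PSRT. On the best reading of the timing, two things blur the answer.

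1. A participant who leaves during weeks 1-2 is in the randomised comparison but cannot show a drug effect. The plan does not say how such people are counted or analysed.
2. For outcomes measured weekly from baseline, the arms can differ only by chance until the first capsule. A smooth curve through those weeks cannot follow an effect that is zero, rises over sessions 3-5 and then levels off. It puts part of the effect in the wrong weeks, and the SAP intends to read arm differences off that curve at chosen times.

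At stake are the size and timing of the estimates. That matters because the trial is meant to supply effect sizes and to help decide whether a larger trial is warranted.

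**Working it through.** **The plan's own figures.** Inputs from the SAP power analysis: 27% vs 43% PPA, 80 participants, an average of 5 assessments each (71% of those after quitting).
- Effect size: 0.16 / (2 × √(0.35 × 0.65)) = 0.168, matching the stated .17.
- 5 / 0.71 ≈ 7 visits, matching the visits in Table 2 at post-quit weeks 1, 2, 4, 8, 10, 16 and 24. All follow the scheduled capsule sessions.
- The stated power of .80 can be neither confirmed nor refuted, because no within-person correlation, alpha or allocation ratio is given. With 40 per arm, two-sided .05 and effective n per arm = 40 × 5 / (1 + 4 × ICC), power is .80 at ICC ≈ 0.11, an effective n of about 138 per arm. That calibration is used next.

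**Part 1: loss before session 3.** Let f be the share lost (assumed).
- Followed, with no drug effect: difference = 16 × (1 − f); N must rise by 1/(1 − f)².
- Counted as smokers in both arms: both rates, and so the difference, are multiplied by (1 − f).
- No post-quit data: the difference stays 16 points; N must rise by 1/(1 − f).

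| | f = 10% | f = 20% |
|---|---|---|
| Difference if followed or counted as smokers | 14.4 points | 12.8 points |
| Power, followed | .72 | .62 |
| Power, counted as smokers | .73 | .66 |
| Power, no post-quit data | .76 | .71 |
| N factor, followed | 1.23 | 1.56 |
| N factor, no post-quit data | 1.11 | 1.25 |

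**Part 2: psychological outcomes.** Visits at protocol weeks 0-7, 9, 13, 15, 21 and 29 (protocol sections 4, 5 and 8). Assumptions: 40 per arm, two-sided .05, random intercept with ICC .5-.7, true arm difference 0 to week 3, one third of 0.50 SD at week 4, two thirds at week 5, and 0.50 SD from week 6.

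Fitting the arm difference by generalised least squares as a quadratic in week t gives −0.033 + 0.0681t − 0.00179t². Truth is 0.50 SD in each row:

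| Protocol week | Quadratic reads (SD) | Power |
|---|---|---|
| 7 | 0.36 | .46-.57 |
| 13 | 0.55 | .80-.88 |
| 15 | 0.59 | .85-.91 |
| 21 | 0.61 | .87-.93 |
| 29 (post-quit week 24) | 0.43 | .51-.52 |

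A straight line shows 0.14 SD at week 0, where the truth is 0, and 0.70 SD at week 29.

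The alternative estimates the difference by visit with k pre-dose scores held equal across arms. The residual variance at one visit is v = 1 − k × ICC² / (1 + (k − 1) × ICC), and SE = √(2v/40).
- k = 3 (weeks 0-2): v = 0.625 at ICC .5 and 0.3875 at ICC .7; 0.50/SE = 2.83 and 3.59; power .81-.95.
- k = 4 (weeks 0-3): v = 0.60 and 0.368; power .82-.96.
- k = 1 (baseline only): power .73-.88.

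The estimate is 0.50 SD in each case.

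The joint test of the two quadratic time-by-arm terms has power about .99 or more here, and .95 or more with a modest random slope added. The single-slope test has power .81 or more.

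**The case against.** - **The primary smoking outcome is outside Part 2.** A reader might infer that weeks with identical arms dilute the main comparison. The documents do not support this: PPA is powered on post-quit visits, and lapse and relapse presuppose a quit attempt in week 5. Table 2 also marks PPA before the quit date, and the SAP does not say whether those visits enter the model. That calls for clarification and does not show dilution.
- **The curve does not always shrink the effect.** It reads low at weeks 7 and 29 and high at weeks 13-21. It is lack of fit in both directions. The SAP also allows an exponential curve; with an assumed form 1 − exp(−t/4) it reads 0.40 SD at week 7 and 0.49-0.52 SD from week 13, much closer to the truth later on.
- **The slope test, which the SAP names first, is little harmed.** This stands. The distortion lies in the time-point contrasts.
- **Early leavers may not dilute anything.** This also stands if they give no post-quit data. The protocol target of 80 who complete all procedures could, read literally, offset the lost numbers. Any dilution works against the drug.
- **The timing is inferred.** No sentence names the randomisation visit, and Table 2 does not place the week-3 questionnaires before or after the capsule.
- **Moving allocation may come too late.** The SAP is dated 6/7/2017 and the protocol expects data collection to end in August 2017, with a 29-week schedule. Moving allocation would also not cure the curve: these are two separate issues with separate remedies.

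**Conclusion.** The concern holds in a limited form. Allocation before session 1 is the best reading, and sessions 1-2 are drug-free and identical in both arms.

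People lost in that interval dilute the PPA difference to 14.4 or 12.8 points at 10% or 20% loss if they are followed or counted as smokers; otherwise they only cost sample size. The loss rates are assumptions, since the documents give none.

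For Aim 2a and the 'a' path only, a quadratic from baseline misreads an assumed 0.50 SD plateau effect as 0.36 SD at week 7, 0.55-0.61 SD at weeks 13-21 and 0.43 SD at week 29. At week 29, which is the SAP's own example time, power is .51-.52, against .81-.95 for a visit-based estimate using weeks 0-2 as common baseline. These figures rest on the assumed effect shape, ICC and 40 per arm. They do not show a general pull toward zero or a weakness of the slope and joint tests.

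This is a cheap improvement to the design and analysis. It does not make the plan invalid.

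**What to change.** 1. State the visit at which participants are randomised. For any not yet allocated, release the allocation at session 3, just before the first capsule.
2. For Aim 2a and the Aim 3 'a' path, treat baseline to week 2 as pre-dose values constrained equal across arms. Add week 3 only where its questionnaires were completed before the capsule. Estimate the arm difference by visit from the first post-dose assessment.
3. State the time origin and visits used in each model, including whether pre-quit PPA visits enter the GLMM. Define the analysis set, including how participants who received no capsule are handled.
4. Report the number lost before session 3 by arm.

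**Cost.** One line in the protocol and a paragraph in the SAP; no new visits or measures. With later allocation, the result applies to people who reach session 3, and some may start PSRT without being randomised. If allocation is already complete, items 2-4 and the statement of the visit can still be done.

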5. MEASURES

Assessment Instruments

Screening Measures

Eligibility Screen. This prescreen questionnaire and telephone-screening will assess inclusion and exclusion criteria.

Motivation to Quit Smoking. This 10-item measure will be used to determine participants' pre-cessation motivation to quit smoking (Rundmo et al., 1997).

Demographics. Participants will be asked to provide standard demographic information (i.e. age, gender, race/ethnicity, level of education, etc.) as well as history of medical problems.

Psychiatric History. Diagnostic exclusions and lifetime prevalence of Axis I diagnoses will be determined by the Structured Clinical Interview for DSM-IV (SCID-NP; First et al., 2007) during the screening. The diagnostic interview will be administered by trained research personnel and will be supervised by the PIs. This interview will serve to contextualize participants' psychiatric history at baseline. In addition, the SCID will be conducted at the final follow-up visit (week 29) in order to assess for changes in diagnoses. Anxiety sensitivity interventions have been shown to aid in the prevention of future mental health disorders, so assessing for changes in diagnostic status in this population will be a useful addition to the literature.

Suicide. The Columbia Suicide Severity Rating Scale (C-SSRS; Posner, Oquendo, Gould, et al. 2007) is a standardized measure of current and past self-injurious behavior, suicidal intent, and suicidal behaviors. The C-SSRS has demonstrated good reliability and validity (Hammad et al., 2006; Posner et al., 2007). The C-SSRS will be administered as part of the diagnostic interview in order to assess for a history of suicide attempts or current suicidal thoughts or plans.

Vital Signs. As part of their screening visit, participants' blood pressure will be assessed.

Laboratory Testing. A study physician will review the patient's medical history and conduct a complete physical examination if deemed necessary. Safety evaluations will also include laboratory tests (CBC, chemistry profile, and thyroid function test). A urine pregnancy test will be performed as part of the general physical medical evaluation of patients during the baseline visit and to assess for study exclusion criteria. In addition, a urine pregnancy test will be performed each month following randomization. Blood draws will be performed(if deemed necessary) in our laboratory

at the University of Texas by a certified phlebotomist and Clinical Pathology Laboratories in Austin will analyze the samples.

Measures of smoking behavior, nicotine dependence, and withdrawal symptoms

Smoking History Questionnaire (SHQ). Smoking history and pattern will be assessed with the SHQ, a 30-item measure that includes items pertaining to smoking rate, age of onset of initiation, years of being a regular smoker, etc. (Brown et al., 2002; [name] et al., 2005). This measure will serve to contextualize the participants' smoking behavior and history at intake.

Fagerström Test for Nicotine Dependence (FTND). The FTND is a 6-item scale designed to assess gradations in tobacco dependence (Heatherton et al., 1991). This measure will serve to quantify nicotine dependence, which will be used as a covariate in the primary analyses.

Nicotine Withdrawal Symptoms. Given its potential relation to outcome, we will monitor withdrawal severity at baseline, weekly throughout treatment and at follow-up assessments, using the Minnesota Withdrawal Scale, a reliable and sensitive 10-item scale (Hughes & Hatsukami, 1986).

Questionnaire of Smoking Urges (QSU). The QSU is a 10-item measure that assesses urges and cravings for cigarettes (Cox et al., 2001). We will monitor craving at baseline, weekly throughout treatment, and at the follow-up assessments. This assessment of urges can be used to evaluate consistency (or lack thereof) with withdrawal symptoms in follow-up tests from the data set.

Smoking Abstinence Expectancies Questionnaire (SAEQ). The SAEQ is a 28-item measure that assesses short-term psychological and physiological consequences to (hypothetically) abstaining from smoking among those that smoke everyday. The measure has 4 internally consistent subscales: Negative Mood, Somatic Symptoms, Harmful Consequences, and Positive Consequences.

Smoking Cessation Self-Efficacy (SE). A participant's confidence that he or she can carry out a behavior such as quitting smoking will be measured at baseline using a well-established 9-item scale developed by Velicer, Diclemente, Rossi, and Prochaska (1990). This instrument includes a subscale regarding confidence in remaining abstinent in negative affect. In previous work, we have successfully used this negative affect subscale for smoking self-efficacy ($\alpha = .85$; [name], Schmidt et al., 2003).

Smoking Cue Appeal Survey (SCAS). The Smoking Cue Appeal Survey (Murray, McHugh, Rowley, Sirota, & [name], 2010) measures cue appeal to sensory smoking cues. An initial study demonstrated good psychometric properties associated with smoking status and craving (Murray et al., 2010).

Barriers to Cessation Scale (BCS). The Barriers to Cessation Scale (Macnee & Talsma, 1995) is a 19-item measure assessing barriers or specific stressors associated with smoking cessation. It has been found to have good internal consistency, good content, and predictive validity (Macnee & Talsma, 1995).

Research Proposal

Smoking Consequences Questionnaire – Brief (SCQ-Brief). The SCQ-Brief is an abbreviated version combining both the Smoking Consequences Questionnaire (SCQ; Brandon & Baker, 1991), an 80-item measure assessing positive and negative smoking outcome expectancies, and the Smoking Consequences Questionnaire - Adult (SCQ-A; Copeland et al., 1995), a 55-item measure considered to be more suitable for adults. The brief version is a 25-item measure that has shown good internal consistency and convergent validity (Rash & Copeland, 2008).

Intolerance for Smoking Abstinence Discomfort (IDQ-Smoking). The IDQ-Smoking questionnaire is a 17-item measure that assesses the intolerance of discomfort associated with recent smoking cessation. The IDQ-S has three reliable components: withdrawal Intolerance, Lack of Cognitive Coping, and Pain Intolerance.

Smoking Status. Self-reports of smoking status will be collected from participants at baseline, weekly throughout treatment and at follow-up assessments. Participant reports of abstinence at all times will be verified by expired carbon monoxide, and additionally at the 8, 10, 16, and 24-week interviews with saliva cotinine (see Table 2). The main outcome analyses are based upon 7-day point prevalence abstinence (i.e., reported abstinence of at least 7 days prior to each scheduled follow-up). Self-report will be overridden by objective verification in the conservative direction (Proceedings of the National Working Conference on Smoking Relapse, 1986).

In addition to point-prevalence outcomes, we also will use the timeline follow-back (TLFB) procedure for assessing the time to first smoking lapse and the time to first relapse, defined as the 7th day on which smoking occurs. The TLFB procedure has demonstrated good reliability and validity (Sobell & Sobell, 1996). The TLFB will be administered at each follow-up to assess cigarette use since the previous assessment.

Biochemical Verification. Self-reported abstinence at the 8, 10, 16, and 24-week follow-ups will be verified by saliva cotinine (cutoff value of 10 mg/ml) for stated abstinence of 2 weeks or more (cotinine may be incompletely metabolized before this time), and carbon monoxide analysis of breath samples (8ppm cutoff) for stated abstinence of 24 hours to 2 weeks (Jarvis et al., 1987). Saliva samples will be frozen and analyzed by an outside laboratory for cotinine level using radioimmune assay. Expired air carbon monoxide levels will be assessed with a Vitalograph Breathco carbon monoxide monitor (Jarvis et al., 1987). Detected values above the stated cutoff scores will be considered indicative of smoking.

Mood, Emotion, and Cognition

Inventory of Depression and Anxiety Symptoms (IDAS). The IDAS is a 64-item measure assessing specific symptom dimensions of major depression and related anxiety disorders (Watson et al., 2007). The scales are internally consistent and show excellent convergent validity and good discriminant validity (Watson et al., 2007).

Difficulties with Emotion Regulation Scale (DERS). The DERS is a 36-item self-report measure of clinically-relevant difficulties in emotion regulation (Gratz & Roemer, 2004). The scale has been validated in cocaine dependent (Fox et al., 2007) and alcohol dependent (Fox, Hong, & Sinha, 2008) populations.

Research Proposal

NEO Five-Factor Inventory (NEO-FFI). The NEO-FFI is a 60-item self-report measure of five basic personality factors (Costa & McCrae, 1989). The measure has been shown to have high test-retest reliability (Robins et al., 2001) and internal consistency (Costa & McCrae, 1992).

Regulatory Focus Questionnaire (RFQ). The Regulatory Focus Questionnaire (RFQ; Higgins et al., 2001) was derived from a factor analysis of items assessing the history of individuals' success at promotion and prevention tasks over the course of their lives.

Sleep, Financial Strain, Life Stressors

Financial Strain Questionnaire (FINSTR). The Financial Strain Questionnaire (Perlin et al., 1981) is a measure of financial strain with 8 items (e.g., "Do you have enough money for the kind of clothing you and your family should have?").

Impulsivity

Delay Discounting. The Delay Discounting Task adapted from Kirby and Marakovic (1996) evaluates the degree to which participants are willing to delay rewards. Participants answer questions that evaluate choice points relative to delaying cash rewards (e.g., Would you rather have \$10 in 30 days or \$2 at the end of the session). Participants will be informed to make their choice as if they were to receive the amount they chose, but that they will not receive additional compensation as part of the study.

UPPS. The UPPS Impulsive Behavior Scale is a 44-item self-report measure of four personality factors hypothesized to underlie impulsive behaviors: sensation seeking, (lack of) premeditation, (lack of) perseverance, and urgency. The measure has demonstrated strong internal consistency reliability for each of the four subscales and has been linked to self-report of risky behaviors (e.g., Whiteside & Lynam, 2003; Whiteside, Lynam, Miller, & Reynolds, 2005). We will use the UPPS-P, a variant of this measure that includes 15 additional items designed to assess positive urgency in addition to negative urgency (Cyders et al. 2007).

Measure of panic severity

Panic Attack Questionnaire (PAQ). The Panic Attack Questionnaire (PAQ) is a commonly-used self-report measure to assess panic attacks. It begins by providing respondents with a definition of panic attacks (according to DSM-III) to create a common understanding of the construct. From there, participants construct their self-assessment. It collects information about participant's frequency of panic attacks and the context in which they arose, as well as intensity of pain symptoms. The final section of the questionnaire consists of open-ended questions about medication use, stress, and treatment received for other illnesses or disorders.

Panic Disorder Severity Scale. The Panic Disorder Severity Scale (PDSS; Shear et al., 1997) is a 7-item, psychometrically-sound clinician-rated instrument for measuring indices of panic severity, including a) frequency of panic attacks, b) distress during panic attacks, c) anticipatory anxiety, d) agoraphobic fear and avoidance, e) interoceptive fear and avoidance, f) impairment of work functioning, and g) impairment of social functioning. Items are rated on a five-point

Likert scale (ranging from 0 [none] to 4 [extreme]) with a total possible score of 28. In the present study, we are employing the PDSS global composite as an index of panic attack severity. Individual items can theoretically be employed in follow-up tests from this same measure (Shear et al., 1997), making it an ideal choice for the current study.

Measures of anxiety sensitivity, distress intolerance, and negative affect

Anxiety Sensitivity Index-III (ASI-III). The ASI-III is a 18-item psychometrically-sound measure of AS whereby participants rate their fear of internal anxiety-related sensations (Taylor et al., 2007).

Distress Intolerance Index (DII). The DII (McHugh & [name], 2010) is a 10-item self-report measure of an individual's perceived ability to tolerate distressing states. This measure was developed in the context of a factor analysis of the most commonly applied measures of distress intolerance, namely the Anxiety Sensitivity Index (Peterson & Reiss, 1992), Distress Tolerance Scale (Simons & Gaher, 2005), and Frustration Discomfort Scale (Harrington, 2005).

Positive and Negative Affect Schedule (PANAS). The PANAS is a 20-item psychometrically-sound mood measure that assesses two global dimensions of affect: positive and negative (Watson et al., 1988).

Brief Pain Inventory (BPI). The BPI short form is a 15-item measure often used in clinical trials. The BPI allows patients to rate the severity of their pain and the degree to which their pain interferes with common dimensions of feeling and function. Initially developed to assess pain related to cancer, the BPI has been shown to be an appropriate measure for pain caused by a wide range of clinical conditions. It is now one of the most widely used measurement tools for assessing clinical pain.

Measures of treatment integrity, safety, and acceptance

Vital Signs. As part of their screening visit, participants' blood pressure and heart rate will be assessed.

Treatment Credibility and Expectancy. The 18-item Treatment Credibility/Expectancy Questionnaire (CEQ; Devilly & Borkovec, 2000) will be used to examine whether treatment expectancy or credibility varied between PSRT+DCS and PSRT+PBO and the relationship between these constructs and treatment response. We will administer the scale after the first treatment sessions of PSRT+DCS and PSRT+PBO protocols.

Patient Adherence. Patient adherence will be assessed by taking attendance at each session. Adherence to the nicotine patch usage will be assessed at Weeks 1-8 following the quit date.

Therapist Adherence. Each session (for those participants who give consent to be videotaped) will be videotaped and 10% will be rated shortly thereafter by independent raters to assess therapist adherence to, and competence with, the treatment protocol. Participants are not required to be videotaped and will indicate on their consent form whether or not they are willing to participate in the recording of sessions.

Research Proposal

Concurrent Treatment. Use of medications other than nicotine patch or other aids to smoking cessation and participation in any concurrent psychotherapeutic treatment will be assessed at each assessment point.

Safety Monitoring and Concerns. At each visit, participants will be asked about side effects of the study medication, nicotine patches, and treatment. Adverse Events and Severe Adverse Events forms will be utilized to track any symptoms expressed during weekly check-ins. Forms will be reviewed each visit by the study PI, and participants who report significant symptoms or adverse reactions will be interviewed separately to determine whether the patch should be discontinued or the dose reduced. Participants who discontinue the patch or change the assigned dose will continue their treatment.

AlcoBreath Screening. At each of the three study visits during which participants are asked to take medication (sessions 3-5), participants will be asked to breathe into an AlcoBreath tube in order to assess for the presence of alcohol before they are administered the study medication.

Facial recognition task

At baseline and follow-up participants will complete a computerized task that takes approximately 5-8 minutes. The task is currently in use in our lab (IRB: 2016_02_0139). Facial stimuli depicting the same adult Caucasian male with either a fearful or a calm facial expression will be selected from the standardized and validated NimStim Faces Set (Tottenham et al., 2009). Morphing software for Windows (Version 3.1, M. Fujimiya) was used to nonlinearly morph the images in 10% increments from the extreme ends (0% to 100%) between two identities, or within the same identity between neutral and fearful facial expression. The fearfulness morphs are the same identity changing on expression of fear. The “target” is the facial stimulus that must be recognized, which is the fearful face (100% morph). The learning phase involves eight 2-second presentations of the target stimulus. Following each presentation, participants are shown another facial stimulus and asked to identify whether it is the same as the target. In the memory phase of the experiment, there are five blocks of 12 randomly presented facial stimuli (11 morphs and 1 completely different identity) and participants have to identify which are the same as the target from the previous phase. The purpose of the first phase is for participants to learn procedures and the target image. The purpose of the second phase is to test for generalization of recognition to the morphs that resemble the target images on a gradient of emotional expression or identity. Participants’ responses and reaction times are recorded.

Assessment Schedule

Participants will receive thorough assessments prior to and over the course of this study. The schedule of assessment visits is such that it allows us to (1) compare smoking cessation outcomes in the present study to that observed in previous studies and (2) carefully examine the proposed therapeutic mechanisms of action. A tabular synopsis of the intervention and assessment data collected throughout the study is provided in the table below.

Research Proposal

Table 2. Schedule of assessments											
Protocol Weeks	>-3	-2	0	1-2	3	4	5	6	7	9	13-29
Measures	Pre-Screen	Screening Assessment	Baseline				WK 0 Quit Week	WK 1	WK 2	WK 4	WK 8, 10, 16, 24
Screening											
Demographics	X	X									
Smoking history*	X	X									
Motivation to quit smoking* (20 items)		X									
SCID		X									X (week 29)
Medical history		X									
